## **8.3 Study Treatment Assignment**

Subjects will be randomized between the 2 treatment arms.

## **8.4 Blinding**

NOT APPLICABLE

## 8.5 Treatment Accountability and Compliance

The investigation site will maintain records of study drug (investigational product) delivered to the study site; the inventory at the site; the distribution to and use by each subject; and the return of study drug to the Sponsor for storage and/or disposal. These records should include dates, quantities, batch/blister card/pouch/serial numbers, expiration dates, in-clinic temperature log(s), and unique code numbers assigned to the study drug and study subjects.

At each visit after initiation of treatment, site staff will record compliance of subjects with their assigned regimen. Subjects will be instructed to bring their study drug pouches containing unused/partially used/empty blister cards back for inspection at each study visit. Subjects are to be reminded of the importance of compliance with their assigned regimen, with an emphasis on taking their study drug on schedule and maintaining the prescribed interval between doses.

Investigators will maintain records that document adequately that the subjects were provided with the correct study drug kits and will reconcile the products received from the drug dispensing center. Study drug will not be returned to the Sponsor or destroyed at the clinical site until accountability has been fully determined.

Medication containers must be returned at each visit, as compliance will be assessed by tablet counts. Noncompliance is defined as taking less than 80% or more than 120% of study drug during any outpatient evaluation period (visit to visit). Discontinuation for noncompliance is at the investigator's discretion and is to be noted on the eCRF.

## 8.6 Prior and Concomitant Illnesses and Medications

Investigators should document all prior significant illnesses that the subject has experienced within 5 years prior to screening. Medical histories with ongoing or worsening condition before 5 years prior to screening may be documented per investigator's discretion. Additional illnesses present at the time when informed consent is given and up to the time of first dosing are to be regarded as concomitant illnesses. Illnesses first occurring or detected during the study and/or worsening of a concomitant illness during the study are to be documented as AEs on the eCRF.

### 8.6.1 Permitted Treatment

- Full supportive care is to be administered per normal or routine practice at the study center. Concomitant anti-cancer therapy is not permitted. Palliative and supportive care for disease-related symptoms will be allowed to subjects in this study (e.g. bisphosphonates). However, subjects requiring palliative radiation anti-cancer therapy will be removed from the study.

- Subjects are required to continue the LHRH super-agonists/antagonists (if currently receiving this therapy prior to Cycle 1, Day 1) therapy unless having undergone bilateral orchiectomy.
- Standard therapies for concurrent medical conditions, such as if the subject is taking a regimen for pain control under physician supervision.
- Treatment for nausea, vomiting, and diarrhea, should they occur is allowed, using standard agents per institute's standard of practice. Tylenol and over the counter NSAIDs are also allowed.
- Subjects may receive antibiotics for infections that might occur

### 8.6.2 Prohibited Treatment

- Glucocorticoids and herbs known to alter PSA levels (saw palmetto or PC-SPES)
- Any concurrent chemotherapy, radiotherapy, hormonal therapy (AR antagonists.), or immunotherapy
- Inducers or inhibitors of CYP3A4, or sensitive CYP3A substrates (detail see appendix 4)
- Other investigational agents

### 8.6.3 Dose modification and missing dose

Treatment modifications will be made based on specified safety criteria. Subjects may skip or discontinue treatment with GT0918 if they experience at least one adverse event, (noted below), following their dose of GT0918, and are considered by the Investigator to be **“possibly”**, **“probably”** or **“definitely”** related to study drug. Treatment modifications must be reported to the project team and discussed with the assigned medical monitor.

- 1) For any subjects experiencing grade 3 or 4 hematologic and/or biochemical toxicity, study drug will be temporarily interrupted until toxicity resolves to grade 1 or better
- 2) For any subjects experiencing grade 2 non-hematologic toxicity with significant impact on subject's daily active life, such as asthenic condition (including asthenia and fatigue), hepatotoxicity, mental impairment and anxiety, study drug will be temporarily interrupted until toxicity resolves to grade 1 or better
- 3) If the Investigator considers that continuing study drug is clinically beneficial for the subjects, the treatment and dose can be resumed. For some subjects if dose reduction is safe and clinically appropriate, a dose range of 25-50% dose reduction from original starting dose can be considered. The dose modification and schedule must be

Suzhou Kintor Pharmaceutical, Inc.  
Protocol#: GT0918-US-1002

Proxalutamide (GT0918)

discussed prior to implementation with the assigned medical monitor. Possible dose reductions are proposed as follow.

- i. For dose cohort of 400mg: starting dose can be 200mg or 300mg
- ii. For dose cohort of 500mg: starting dose can be 300mg or 400mg

**Dose restoration:** If any subjects on reduced dose for 2 cycles or more, the subject will have an option for the dose modification, for example, either to remain on the same dose or increase one dose level up or resume initial dose. The dose modification shall be considered based on investigator's clinical judgement for the best interest and care of subject and it must be discussed with medical monitor before implemented and document CRF timely and properly.

The subject may discontinue study drug for up to 5 consecutive days without being discontinued for noncompliance, which is at the investigator's discretion and is to be noted on the eCRF.

Study drug GT0918 is administrated orally once per day on empty stomach at least one hour before or 2 hours after a meal. Subjects are recommended to take GT0918 on the same time of the day during entire treatment. In case there is accidentally a missing dose of study drug on usual dosing time, the subject may take the drug as soon as possible within 8 hours. If the drug cannot be taken within 8 hours of the scheduled dosing time, the subject should omit the dosing on that day and report missing dose in CRF. However, a subject is not allowed to have "missing doses" in consecutive days unless he has intolerable toxicities and is requested by investigator for study drug interruption.

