### **13.6 Safety Analysis**

Assessment of safety will be based on the incidence of AEs, AEs resulting in discontinuation, and serious adverse events (SAEs) in each dose level. AEs will be coded using the Medical Dictionary for Regulatory Activities (MedDRA). Summaries of AEs will be provided showing the number and percentage of subjects who experienced at least 1 AE. These summaries will be presented by dose level, system organ class, and the preferred term. The occurrence of AEs will also be tabulated by severity and relationship to study medication. SAEs and AEs resulting in discontinuation will be summarized separately. All vital sign measurements, clinical laboratory results, pain score, and ECG findings will be summarized by dose level and time point using descriptive statistics or frequency distributions.

All safety summaries will be performed by dose levels and by all subjects.

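### Investigator-directed holds and reductions can count as noncompliance under Section 8.5, the pause rules in 8.6.3 conflict, and 13.6 plans no by-arm summary of dose modifications

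*Combined protocol and SAP*

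**What the plan says.** - **Pause (8.6.3).** "The subject may discontinue study drug for up to 5 consecutive days without being discontinued for noncompliance". The sentence leaves this to the investigator and asks for an eCRF note, but requires no toxicity or other reason.
- **Missed doses (8.6.3, last paragraph).** Missed doses are not allowed "in consecutive days unless he has intolerable toxicities and is requested by investigator for study drug interruption".
- **Toxicity holds (8.6.3).** For the listed drug-related toxicities, "study drug will be temporarily interrupted until toxicity resolves to grade 1 or better". No maximum length is given.
- **Reductions (8.6.3).** The 400 mg arm may go to 300 or 200 mg, and the 500 mg arm to 400 or 300 mg.
- **Compliance (8.5).** At each visit "site staff will record compliance of subjects with their assigned regimen", and "compliance will be assessed by tablet counts". The threshold reads: "Noncompliance is defined as taking less than 80% or more than 120% of study drug during any outpatient evaluation period (visit to visit". On the consequence: "Discontinuation for noncompliance is at the investigator's discretion and is to be noted on the eCRF".
- **Withdrawal (7.3).** Drug noncompliance is an example under protocol deviation. Toxicity is a separate reason.
- **Analysis (5.1, 13.6).** The primary endpoint is the choice of RP2D, resting on safety, tolerability and exposure. Among actions on study drug, 13.6 covers only permanent stopping: "SAEs and AEs resulting in discontinuation will be summarized separately".

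**The concern.** In a trial that allows dose modification, interruptions and reductions are a main sign of how well a dose is tolerated. Section 8.5 counts tablets without asking why a tablet was not taken. A subject who follows an ordered hold can therefore fall into the same category as one who forgets his tablets. If he then leaves the study, Section 7.3 offers a heading, protocol deviation, under which his exit need not reach the table of AE discontinuations.

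The comparison of 400 mg with 500 mg is what the RP2D choice needs. If sites classify the same event differently, or if modifications are never tabulated, that comparison loses information on two things the primary endpoint names: tolerability and exposure.

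**Working it through.** The plan gives no figure of its own to reproduce here. The check applies its stated limits to its stated schedule.

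**Inputs.** The noncompliance limit is 80% per visit interval (8.5). Pill counts fall at Cycle 1 Day 15 and Cycle 2 Day 1, which is study day 29 (9.2.2), so Cycle 1 has two 14-day intervals. Later intervals are 28 days. Reduced doses are from 8.6.3, and 30 subjects per arm is from 13.1. I assume nominal visit days, a hold that lies within one interval, and every other dose taken.

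**Step 1: days off.** Share taken = (L − d)/L, with L the interval length and d the days off. It is below 0.80 when d > 0.2L, that is d > 2.8 for L = 14 and d > 5.6 for L = 28.

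| Interval | Days off | Share taken | Below 80%? |
|---|---|---|---|
| 14 days | 2 | 12/14 = 85.7% | no |
| 14 days | 3 | 11/14 = 78.6% | yes |
| 14 days | 5 | 9/14 = 64.3% | yes |
| 28 days | 5 | 23/28 = 82.1% | no |
| 28 days | 6 | 22/28 = 78.6% | yes |

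A directed hold of 3 or more days in a Cycle 1 interval, or of 6 or more in a later one, meets the definition. The tolerated 5-day pause stays above the limit in a 28-day interval and falls below it in a 14-day one.

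**Step 2: reductions.** Section 8.5 does not say whether the reference is the randomised dose or the dose now prescribed. For a full interval on the reduced dose, taken as prescribed:

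| Change | Against randomised dose | Against current dose |
|---|---|---|
| 400 to 300 mg | 75% (below) | 100% |
| 400 to 200 mg | 50% (below) | 100% |
| 500 to 400 mg | 80% (not below) | 100% |
| 500 to 300 mg | 60% (below) | 100% |

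On the first reading three of four are noncompliant; on the second, none.

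**Step 3: the two sentences in 8.6.3.** Take a pause of 2 to 5 days without toxicity. The pause sentence tolerates it, and the missed-dose sentence does not allow it. For a toxicity interruption that the investigator requests, the two do not conflict.

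**Step 4: what misfiling could do.** With 30 per arm, one subject moved out of AE discontinuations changes that arm's rate by 1/30 = 3.3 points. For illustration, assume true toxicity-driven discontinuation of 10% at 400 mg and 30% at 500 mg (neither figure is in the documents), with shares m4 and m5 misfiled. The observed difference in points is 30(1 − m5) − 10(1 − m4).

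| m4 | m5 | Observed difference |
|---|---|---|
| 0 | 0 | 30 − 10 = 20 |
| 25% | 25% | 22.5 − 7.5 = 15 |
| 50% | 50% | 15 − 5 = 10 |
| 50% | 0 | 30 − 5 = 25 |
| 0 | 50% | 15 − 10 = 5 |

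The difference can shrink or grow, depending on shares that nobody knows.

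**The case against.** **The rules mostly fit together.** A reader might infer that the pause, missed-dose, hold and compliance rules all contradict one another. They do not. The missed-dose rule exempts toxicity interruptions that the investigator requests, and the 5-day sentence does not cap toxicity holds. A subject at 64.3% after a 5-day pause can be flagged under 8.5 and still protected from removal by 8.6.3, which is how an exception works. This stands. The direct conflict is limited to pauses of 2 to 5 days without toxicity. The exemption in the missed-dose rule is, however, not carried into 8.5, where noncompliance is defined.

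**Toxicity is captured elsewhere.** Section 12.5.1 records the action taken with study drug for every AE. The synopsis and 8.6.3 send modifications to the medical monitor. Section 7.3 has its own toxicity heading, and stopping for noncompliance is discretionary. The AEs themselves are tabulated by severity and relationship. This stands too: nothing directs an investigator to file an ordered hold as noncompliance. But these safeguards show that the data exist. They supply neither a classification rule nor a table.

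**A later SAP may add the table.** Section 13 promises a SAP that overrides the protocol, and full listings. The documents contain no separate SAP text, so it cannot be shown that no summary will be made. Listings are still not a comparison by arm.

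**Other inferences that go too far.** The half-life in 9.2.6 might suggest long holds, but no figure links residual drug level to the time a toxicity takes to resolve. Loss of subjects from the Per Protocol set might also be inferred, but nothing classes compliance under 80% as a major violation, and safety is analysed in the Safety Analysis Set.

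**Conclusion.** The concern holds in a limited form. Three things follow from the text: the two sentences in 8.6.3 conflict for pauses without toxicity; 8.5 has neither an exemption for directed holds nor a stated denominator after a reduction; and 13.6 lists no by-arm summary of exposure, interruptions or reductions. The literal thresholds are 3 days in a 14-day interval and 6 days in a 28-day interval. The result for reductions rests on reading the reference regimen as the randomised dose.

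How often misclassification would occur is unknown; it is a risk, not a necessary result. A reader might infer that the dose causing more holds will look better tolerated than it is. The documents do not support that direction. On the randomised-dose reading, the smallest reduction is flagged in the 400 mg arm (75%) and not in the 500 mg arm (80%), so flagging differs between arms for a reason unrelated to which dose causes more holds. The supportable statement is that the comparison can be distorted either way. The point should be corrected because it touches the primary endpoint and is cheap to put right.

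**What to change.** 1. **Reconcile 8.5 with the pause, missed-dose and hold text in 8.6.3**, so that one event has one classification at every site. Which clinical rule applies is for the sponsor and investigators, and none is proposed here.
2. **In 8.5, define compliance** as tablets taken divided by tablets prescribed at the current dose, leaving out investigator-directed hold days. Record such holds and reductions as dose modifications for an AE, not as noncompliance.
3. **In 13.6, report by randomised arm**, beside AE discontinuations: subjects with an AE-driven interruption or reduction, days held, and mg taken over mg planned in Cycles 1 to 6. Fix planned mg at the randomised dose, and state how days after permanent discontinuation are handled. This denominator differs from that in item 2 on purpose: compliance asks whether the subject took what was prescribed, while dose intensity asks how much of the randomised dose was delivered.

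Cost: wording in the protocol and SAP, one derived variable, and possible re-coding of events already entered as noncompliance. Pill counts and the AE action field are already collected, so no new data are needed.

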## 9 STUDY PROCEDURES

The Schedule of Assessments (Appendix 1) outlines the timing of procedures, and assessments to be performed throughout the study.

### 9.1 Subject Informed Consent

Prior to performing any study-related procedures, the Investigator (or his/her designated staff member) will obtain signed written informed consent from the subject.

### 9.2 Expanded/Phase II Study Visits

#### 9.2.1 Screening Visit

Screening Visit (days -21 to -1) will occur within 3 weeks prior to Day 1. Re-screening is allowed for some special cases where clinical reassessments are required and approved by medical monitor. Assessments performed as part of standard of care and obtained prior to

informed consent but within 28-days of enrollment may be used in some cases to satisfy the screening criteria. The following assessments and tests will be performed:

- Informed consent
- Inclusion/Exclusion Criteria
- Demographics, Medical and Surgical History
- Schedule CT or MRI, or/and bone scan preferably within -7 days of Day 1 of treatment

OR

Document/Assess Disease Status (Obtain CT or MRI or/and bone scan that may be performed as part of standard care within 6 weeks prior to Day 1 to confirm screening requirements)

- Vital Signs, including Height and Body Surface Area (BSA) (Screening only)
- Complete Physical Exam
- ECOG performance status
- Laboratory Tests (fasting where applicable): hematology, PT/PTT/INR, chemistry including electrolytes, urinalysis, lipid profile and blood glucose, PSA, LDH, and testosterone
- 12 lead ECG
- Assess Prior/Concomitant medication usage. If pain medications are taken, list name, dosage, frequency, etc.

### 9.2.2 On-Treatment Visits

#### Cycle 1, Day 1 (Week 1) before dosing for ALL subjects

- Admit to Clinical Research Unit (CRU)
- Confirm screening eligibility test results are acceptable for study participation
- Review and record Interim Medical and Surgical History (prior to first dose)
- Vital signs (prior to first dose)

Suzhou Kintor Pharmaceutical, Inc.  
Protocol#: GT0918-US-1002

Proxalutamide (GT0918)

- Abbreviated Physical Exam
- ECOG (prior to first dose)
- Laboratory Tests (fasting where applicable): hematology, chemistry & electrolytes, urinalysis, lipid profile and blood glucose, PSA, and LDH
- 12 lead ECG
- Assess AEs
- Assess Concomitant Medication usage/confirmation. If pain medications are taken, list name, dosage, frequency, etc.
- Study drug disposition
- Exploratory markers: circulating tumor cells (CTC), ct-DNA and ct-RNA

#### Cycle 1 Day 15

- Subject returns to CRU
- Vital Signs
- Abbreviated Physical exam
- ECOG
- Assess for AEs
- Assess compliance by pill count
- Assess concomitant meds usage/confirmation. If pain medications are taken, list name, dosage, frequency, etc.
- Study drug disposition

#### Cycle 2 Day 1 (Study day 29)

- Subject returns to CRU
- Vital signs
- Abbreviated Physical Exam

Suzhou Kintor Pharmaceutical, Inc.  
Protocol#: GT0918-US-1002

Proxalutamide (GT0918)

- ECOG performance status
- Laboratory Tests: hematology, chemistry & electrolytes, lipid profile and glucose, PSA, LDH, testosterone, and urinalysis
- 12-lead ECG
- Assess AEs
- Assess Concomitant Medication usage/confirmation. If pain medications are taken, list name, dosage, frequency, etc.
- Assess compliance by pill count
- Study drug disposition

#### Cycle 3 Day 1 (Study day 57)

- Subject returns to CRU
- Vital signs
- Abbreviated Physical Exam
- ECOG performance status
- Laboratory Tests: hematology, chemistry & electrolytes, lipid profile and glucose, PSA, LDH, testosterone, and urinalysis
- Assess AEs
- Assess Concomitant Medication usage/confirmation. If pain medications are taken, list name, dosage, frequency, etc.
- Assess compliance by pill count
- Study drug disposition

#### Cycle 4 Day 1 Study day 85

- Subject returns to office/CRU
- Vital signs
- Complete Physical Exam

Suzhou Kintor Pharmaceutical, Inc.  
Protocol#: GT0918-US-1002

Proxalutamide (GT0918)

- ECOG performance status
- Laboratory Tests: hematology, chemistry & electrolytes, lipid profile and glucose, PSA, PT/PTT/INR, LDH, testosterone, urinalysis
- Assessment of exploratory markers: circulating tumor cells (CTC), ct-DNA and ct-RNA, and androgen receptor (AR) related gene profiles
- 12-lead ECG
- CT/MRI, Bone Scan
- Assess AEs
- Assess Concomitant Medication usage/confirmation. If pain medications are taken, list name, dosage, frequency, etc.
- Assess compliance by pill count
- Study drug disposition
- Exploratory Markers

#### Cycle 5 Day 1 Study day 113

- Subject returns to office/CRU
- Vital signs
- Abbreviated Physical Exam
- ECOG performance status
- Laboratory Tests: hematology, chemistry & electrolytes, lipid profile and glucose, PSA, LDH, testosterone, and urinalysis
- Assess AEs
- Assess Concomitant Medication usage/confirmation. If pain medications are taken, list name, dosage, frequency, etc.
- Assess compliance by pill count
- Study Drug disposition

Suzhou Kintor Pharmaceutical, Inc.  
Protocol#: GT0918-US-1002

Proxalutamide (GT0918)

Cycle 6 Day 1 Study day 141

- Subject returns to office/CRU
- Vital signs
- Abbreviated Physical Exam
- ECOG performance status
- Laboratory Tests: hematology, chemistry & electrolytes, lipid profile and glucose, PSA, LDH, testosterone, and urinalysis
- Assess AEs
- Assess Concomitant Medication usage/confirmation. If pain medications are taken, list name, dosage, frequency, etc.
- Assess compliance by pill count
- Study drug disposition

Study day 169 (if eligible for continuous treatment, this will be Cycle 7 Day 1)

- Subject returns to CRU
- Disease Assessment scans (CT or MRI or bone scan).
- Vital signs
- Complete Physical Exam
- ECOG performance status
- Laboratory Tests: hematology, chemistry & electrolytes, lipid profile and glucose, PSA, PT/PTT/INR, LDH, testosterone, urinalysis,
- 12-lead ECG
- Exploratory markers: circulating tumor cells (CTC), ct-DNA and ct-RNA
- Assess AEs
- Assess Concomitant Medication usage/confirmation. If pain medications are taken, list name, dosage, frequency, etc.

- Assess compliance by pill count
- Study drug disposition (if on Cycle 7 Day 1)

### **9.2.3 Expansion Study (Additional Cycles after Cycle 6 Day 28 (Cycle 7 Day 1, to Cycle 30 Day 28)**

Eligible subjects (no disease progression) have the option to continue additional cycles (up to 18 more cycles) on their assigned dose level until they exhibit PD and/or investigator discretion. Visits will occur every cycle/month, i.e. every 28 days (+/- 3 days). Every 3 cycles, the subjects will be given a disease assessment scan (CT and/or MRI or bone scan). Every 6 cycles, the subjects will be assessed by Investigator and discussed with Medical Monitor or/and Sponsor to determine whether to proceed into the next 6 cycles.

- Subject returns to office
- Disease Assessment scans (CT or MRI or bone scan) are to be performed every 3 cycles (84 +/- 14 days, Cycle 7 Day 1, Cycle 10 Day 1, Cycle 13 Day 1, Cycle 16 Day 1, Cycle 19 Day 1, Cycle 22 Day 1, Cycle 24 Day 28, Cycle 27 D28 and Cycle 30 D28).
- Vital signs
- Complete Physical Exam (Every 3 cycles on Cycle 7 Day 1, Cycle 10 Day 1 Cycle 13 Day 1, Cycle 16 Day 1, Cycle 19 Day 1, Cycle 22 Day 1, Cycle 24 Day 28, Cycle 27 D28 and Cycle 30 D28)
- Abbreviated Physical Exam (Cycle 8 Day 1, Cycle 9 Day 1, Cycle 11 Day 1, Cycle 12 Day 1, Cycle 14 Day 1, Cycle 15 Day 1, Cycle 17 Day 1, Cycle 18 Day 1, Cycle 20 Day 1, Cycle 21 Day 1, Cycle 23 Day 1, Cycle 24 Day 1, Cycle 26 Day 1, Cycle 27 Day 1, Cycle 29 Day 1, Cycle 30 Day 1)
- ECOG status
- Laboratory Tests: hematology, chemistry & electrolytes, testosterone, PSA, and urinalysis, lipid profile/blood glucose performed every 3 months (For subjects with abnormal lipid profiles monthly testing is required.)
- 12-lead ECG (every 3 cycles on Cycle 7 Day 1, Cycle 10 Day 1 Cycle 13 Day 1, Cycle 16 Day 1, Cycle 19 Day 1, Cycle 22 Day 1, Cycle 25 Day 1 and Cycle 28 Day 1 )

Suzhou Kintor Pharmaceutical, Inc.  
Protocol#: GT0918-US-1002

Proxalutamide (GT0918)

- Exploratory markers (every 3 cycles on Cycle 7 Day 1, Cycle 10 Day 1, Cycle 13 Day 1, Cycle 16 Day 1, Cycle 19 Day 1, Cycle 22 Day 1, Cycle 25 Day 1 and Cycle 28 Day 1)
- Administer study drug from subject supply in the office
- Study drug disposition (unless this is the last visit of the extension study)
- Assess AEs
- Assess Concomitant medication usage/confirmation. If pain medications are taken, list name, dosage, frequency, etc.
- Assess compliance by pill count

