### 13.4 Efficacy Analysis

#### Assessment of Efficacy Variables:

1. Assessment of PSA: Blood samples will be collected to determine the serum total PSA concentration.
2. Change of PSA from baseline:
  - a. The percentage of change of PSA from baseline Week 12 will be calculated. Maximum percentage change of PSA from baseline at any time will be calculated.
  - b. The proportion of subjects achieving a  $\geq 50\%$  reduction in PSA at 3 months (12 weeks) as compared to baseline (study entry) will be determined.
3. Assessment of soft tissue and bone:
  - c. Soft tissue: Chest, abdomen, and pelvic CT, or MRI (if CT not possible), will be performed. Changes in the size of target lesions will be evaluated.
  - d. Bone scan: Radionuclide bone scan will be performed. Changes in the number of lesions will be reported.
  - e. Skeletal-related events: Severity of skeletal-related event (bone pain, analgesia intake) will be assessed monthly per PCWG2.
4. Symptomatic progression will be evaluated by type. Symptomatic progression is defined as evidence of unequivocal symptomatic or clinical progression defined by at least 1 of the following:
  - A marked escalation in cancer-related pain that is assessed by the Investigator to indicate the need for other systemic therapy or palliative radiotherapy. Ignore early changes ( $\leq 12$  weeks) in pain or health-related quality of life in absence of compelling evidence of disease progression. Confirm progression of pain or health-related quality of life  $\geq 3$  weeks later,

- An immediate need for initiation of new anticancer treatment, surgical or radiological intervention for complications due to tumor progression,
- A marked deterioration in ECOG performance status to Grade 3 or higher, or
- Performance status: ECOG performance status will be assessed. Changes from baseline will be evaluated.

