#### Method of assessment

The same method of assessment and the same technique should be used to characterize each identified and reported lesion at baseline and during follow-up. Imaging based evaluation should always be done rather than clinical examination unless the lesion(s) being followed cannot be imaged but are assessable by clinical exam.

Clinical lesions:

- Clinical lesions will only be considered measurable when they are superficial and  $\geq 10$  mm diameter as assessed using calipers (e.g. skin nodules). For the case of skin lesions, documentation by color photography including a ruler to estimate the size of the lesion is suggested. As noted above, when lesions can be evaluated by both clinical exam and imaging, imaging evaluation should be undertaken since it is more objective and may also be reviewed at the end of the study.

CT, MRI:

- CT is the best currently available and reproducible method to measure lesions selected for response assessment. This guideline has defined measurability of lesions on CT scan based on the assumption that CT slice thickness is 5 mm or less. When CT scans have slice thickness greater than 5 mm, the minimum size for a measurable lesion should be twice the slice thickness. If there is concern about radiation exposure or dye with CT, MRI may be used instead of CT in selected instances.

Ultrasound:

- Ultrasound is not useful in assessment of lesion size and should not be used as a method of measurement. Ultrasound examinations cannot be reproduced in their entirety for independent review at a later date and, because they are operator dependent, it cannot be guaranteed that the same technique and measurements will be taken from one assessment to the next. If new lesions are identified by ultrasound in the course of the study, confirmation by CT or MRI is advised.

Endoscopy, laparoscopy:

- The utilization of these techniques for objective tumor evaluation is not advised. However, they can be useful to confirm complete pathological response when biopsies

are obtained or to determine relapse in trials where recurrence following complete response or surgical resection is an endpoint.

Tumor markers:

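### The imaging instructions conflict: some sections plan both CT/MRI and bone scan, but the visit lists and Schedule footnote 3 allow one, so radiographic progression can be missed or dated late

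*Combined protocol and SAP*

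**What the plan says.** Three groups of text in the protocol govern disease imaging.

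- **Both modalities.** Section 5.2 (Secondary Endpoints) has CT/MRI together with bone scans every 12 weeks, to determine time to progression and the percentage progressed at 6 and 12 months. Section 9.2.2, Cycle 4 Day 1, lists "CT/MRI, Bone Scan". Section 13.4 has "Soft tissue: Chest, abdomen, and pelvic CT, or MRI (if CT not possible), will be performed" and, separately, "Bone scan: Radionuclide bone scan will be performed. Changes in the number of lesions will be reported". The Synopsis paragraph on efficacy variables matches 13.4.
- **Any one modality.** The Day 169 list in 9.2.2 reads "Disease Assessment scans (CT or MRI or bone scan", with the bracket closing there. The visit list in 9.2.3 reads "Disease Assessment scans (CT or MRI or bone scan) are to be performed every 3 cycles". The opening paragraph of 9.2.3 varies it: "the subjects will be given a disease assessment scan (CT and/or MRI or bone scan". Footnote 3 of the Schedule of Assessments (16.1) also offers the three as alternatives, at screening and every 3 cycles.
- **Ambiguous.** The Synopsis (methods of assessing progression) joins CT and bone scan with *and/or*. Section 9.2.1 (Screening) uses *or/and*.

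No section ties the choice of modality to a subject's baseline sites of disease.

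**The concern.** Section 13.3 expects subjects with bone disease, soft-tissue disease and both, and the Synopsis assesses them by RECIST and PCWG-2 criteria. In a subject with disease in both compartments, one modality cannot show that neither has progressed. The study is open-label at 10 centers, so the choice of scan may vary by site and investigator, and the radiographic endpoints could partly reflect scanning habit. Footnote 3 also withholds additional cycles until absence of progression is confirmed, and that check rests on the same scans.

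**Working it through.** The plan states no figure to reproduce. The check is a count of imaging visits, followed by a reading of the response tables.

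**1. Imaging visits.** Cycles last 28 days, so Day 1 of cycle n is study day 28(n − 1) + 1, and Day 28 of cycle n is study day 28n.

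| Visit | Study day | Wording in visit list |
|---|---|---|
| C4D1 | 28×3 + 1 = 85 | both |
| C7D1 | 28×6 + 1 = 169 | any one |
| C10D1 | 28×9 + 1 = 253 | any one |
| C13D1 | 28×12 + 1 = 337 | any one |
| C16D1 | 28×15 + 1 = 421 | any one |
| C19D1 | 28×18 + 1 = 505 | any one |
| C22D1 | 28×21 + 1 = 589 | any one |
| C24D28 | 28×24 = 672 | any one |
| C27D28 | 28×27 = 756 | any one |
| C30D28 | 28×30 = 840 | any one |

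By the visit lists, 9 of 10 on-treatment points accept a single modality. By footnote 3 it is all 10, plus screening, so the footnote also contradicts the Cycle 4 list.

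**2. Landmarks.** The scans nearest 6 and 12 months are Days 169 and 337. Both carry the alternative wording, as does every visit after Day 85.

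**3. What a skipped scan does to the recorded response** (Appendix 2):

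- *Bone scan skipped, soft-tissue targets measured.* Bone scan is not accepted for measuring lesions and blastic lesions are non-measurable, so bone disease will usually be non-target. Table 1 keeps SD as SD and PR as PR when non-target lesions are not all evaluated, and target CR with non-target lesions not evaluated becomes PR. New bone lesions go unseen. Bone progression can therefore be recorded as stable disease or response.
- *CT/MRI skipped, bone scan done.* Target lesions are not evaluated. Without progression on the bone scan, Table 1 gives NE. The gap is visible, but soft-tissue progression is not dated at that visit.
- *Non-target disease only.* Table 2 gives NE when lesions are not all evaluated.

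**4. Screening.** Appendix 2 treats a lesion found at a location not scanned at baseline as new, hence as progression. A subject screened by CT alone, then given both modalities at Cycle 4, could be called progressed on bone lesions already present at entry. The screening wording therefore matters as well.

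**5. Timing.** Scheduled scans are about 84 days apart (for example 253 − 169 = 84). With no intervening assessment, progression confined to the unscanned compartment would be dated about one interval late, or later still if the same compartment is skipped again.

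**The case against.** The strongest reply is that the protocol already requires both. Section 5.2 says so directly, 13.4 says each will be performed, and the Schedule has a single row covering CT, MRI and bone scan. A site reading the whole document has an instruction to do both, and nothing obliges it to do only one. That stands in part: a reader might infer that progression *is* missed, but the text supports only that it *can* be. It does not remove the conflict, because a site working from the visit lists or footnote 3 can do one scan and comply.

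Other inferences go too far:

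- *The problem starts at Day 169.* Footnote 3 covers screening and Day 85 too.
- *Response is not evaluable whenever a scan is skipped.* Table 1 keeps SD or PR when only non-target lesions are missed.
- *Detection is delayed by at least 12 weeks.* Section 8.2 allows another PSA or tumor assessment after 4–6 weeks for a mixed response, 9.2.5 allows unscheduled assessments, and scans have a 14-day window either side in 9.2.3 and footnote 3.
- *Appendix 2 demands both scans every time.* Its rule, "The same method of assessment and the same technique should be used to characterize each identified and reported lesion at baseline and during follow-up", applies lesion by lesion. It argues against dropping the modality that identified a baseline lesion, but does not itself require imaging of two compartments at each visit.

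**Conclusion.** The contradiction is confirmed and should be corrected. It touches rPFS, time to radiographic progression, the percentage progressed at 6 and 12 months, and the no-progression check before further cycles. The effect on objective response is narrower, through the Table 1 routes above. The primary objective (safety, tolerability and dose selection) is unaffected. Sections 13 and 13.1 give no hypothesis test or power for the imaging endpoints, and both arms follow the same rule.

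The bias cannot be sized from the documents. A reader might multiply three guesses: the share of progressions confined to one compartment, the share of visits with one modality, and the chance that it is the wrong one. Assuming 30–50%, 20–100% and one half gives anything from 0.30 × 0.20 × 0.5 = 3% to 0.50 × 1.00 × 0.5 = 25% of progressions missed at a visit. None of these inputs is in the protocol, and choosing a modality without regard to known disease sites is itself unsupported. The finding rests on the wording alone.

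**What to change.** - **Protocol.** Bring the Synopsis (methods of assessing progression), 9.2.1, 9.2.2 (Day 169), both places in 9.2.3, and footnote 3 of 16.1 into line with 5.2 and 13.4. At screening and every 12-week assessment, specify CT of chest, abdomen and pelvis (MRI where CT is not possible) *and* radionuclide bone scan, in identical words throughout.
- **Analysis.** Section 13 leaves definitions to the SAP. State there that, for radiographic progression endpoints, a visit missing either modality is not evidence of non-progression, while progression seen on the modality performed still counts. State also how this sits with Appendix 2 Table 1, which would keep SD or PR at some of those visits. This rule is needed even after the wording changes: the Synopsis puts first enrolment in 2Q2019 and version 5.0 is dated 18 March 2021, so visits with one modality may already exist.

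The cost is extra scans only at sites now doing one modality, and somewhat more visits classed as not evaluable. Sections 5.2 and 13.4 already plan both scans, so the imaging burden the protocol intends does not grow.
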